7.6 Alternatives

Alternative therapies include chemotherapy alone, standard chemotherapy/radiation, or no further treatment. Additionally, patients may choose to receive treatment to improve quality of life but which may have no affect on the growth of their cancer. The risks of chemotherapy and standard chemotherapy/radiation include nausea, vomiting, diarrhea, fatigue, bone marrow suppression, and sepsis. The potential benefits of chemotherapy or standard chemotherapy/radiation are prolonged survival. The risk of pursuing no further treatment is tumor progression or spread.

7.7 Compensation

Subjects will not be paid to participate in the study.

8. PHARMACEUTICAL INFORMATION

8.1 Investigational Agent or Device

Not applicable.

8.2 Availability

Not applicable.

8.3 Agent Ordering

Not applicable.

8.4 Agent Accountability

Not applicable.

9. TOXICITIES AND mFOLFIRINOX DOSING AND MODIFICATIONS

9.1 Modified Folfirinox (mFFX) Dosing

Modified Folfirinox dosing is below, **however modifications of dose and schedule are allowed as per clinical judgment of patient's treating medical oncologist.** Recommendations for toxicity management are in Section 9.1.1.

mFOLFIRINOX, 1 cycle = 14 days

- Oxaliplatin 85 mg/m² IV over 2 hours on Day 1, followed by
- Irinotecan 180 mg/m² IV over 90 minutes on Day 1, followed by
- Leucovorin* 400 mg/m² IV over 2 hours on Day 1, followed by
- 5FU** 2,400 mg/m² IV over 46 – 48 hours

*Leucovorin may be administered concurrently with the last 30 minutes of oxaliplatin, and the entire 90 minutes of irinotecan

**5FU is administered via infusion only; there is no bolus injection of 5FU

Subjects should be assessed for Adverse Events (AEs) once during each chemotherapy cycle, and AEs should be recorded in the AE Tracking Form in Appendix V. Serious Adverse Events (SAEs) should be reported promptly as according to the guidelines in this protocol. (See Section 11 for more information regarding documenting and reporting SAEs and AEs.)

Chemotherapy infusion records should be kept in the patient's study chart, either with

the Medication Administration Record (MAR) or other clinic records which contain: Date of infusion, dose completed of each agent, modifications if any and reason for modification with supporting source documents as needed. Laboratory results prior to infusion should also be supplied in the patient study chart, as well as the consultation note if the patient is seen by the treating physician.

Laboratory results and administration dates and doses of each agent should also be entered into REDCap.

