5.3 Randomization to +/- SBRT

Participating centers will submit re-staging scan reports (and images as requested) within 5 business days of the scan's final report date to Stanford, along with documentation of consent. These should be sent in a secure electronic mail message or fax to the PI ([name]) and Clinical Research Coordinator [name] with subject line: "SECURE: STUDY PATIENT FOR RANDOMIZATION". Stanford research staff will randomize the subject by participating site and within the next business day, will send an electronic message to the PI and Research Coordinator from the participating center with the outcome and instructed treatment plan.

Randomization will be done with R software, a randomized block design. It will be performed by a Stanford Statistician or the Stanford study coordinator who will maintain a password-protected list and assign patients to the treatment arms as each patient is enrolled at each institution. Randomization Arm will be confirmed by two coordinators prior to electronic notification and written documentation (Note to File) of the treating physician and outside research coordinators.

Subjects **randomized to SBRT** are allowed up to an 8-week break between induction chemotherapy and radiation treatments.

Subjects **randomized to mFOLFIRINOX** can continue directly with that treatment. Any breaks between mFOLFIRINOX cycles will be determined by the treating Medical Oncologist and are permitted for up to 8 weeks.

If a subject exceeds the allowable 8-week break between treatments, s/he may continue treatment “off protocol” and as recommended by the treating Medical Oncologist or according to local standard of care. These subjects will be followed for overall survival and progression-free survival. Subsequent data analysis will be performed on an intention-to-treat basis.

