6.2 SBRT Treatment Delivery

All patients will receive 5 fractions of 8 Gy allowing up to 30% dose heterogeneity, delivered over a five-day period (ideally all 5 fractions should be delivered Monday through Friday however the 5 fractions may be delivered over 2 weeks as long as the patient receives at least 2 fractions per week). SBRT treatment planning and delivery must be completed at a participating site. The recommended interval between induction chemotherapy followed by SBRT and between SBRT followed by chemotherapy is 2-4 weeks. However, it is acceptable to administer SBRT and chemotherapy within 8 weeks of each other.

If a patient is unable to adhere to the protocol schedule for SBRT treatment, the patient will continue treatment off protocol and as recommended by the treating Medical Oncologist or according to local standard of care. These patients will be followed for overall survival. Subsequent data analysis will be performed on an intention-to-treat basis.

All patients must start SBRT within 4 weeks of the simulation scan and may have up to an 8-week break between radiation and chemotherapy.

For LINAC-based, treatment should entail:

- 1) Initial patient positioning based on either kV or volumetric kV (cone-beam CT) imaging with shifts to bony anatomy as appropriate.
- 2) Orthogonal kV/MV or kV/kV projection imaging to verify the location of the fiducials prior to delivery of first treatment beam. A secondary shift based on the location of fiducials may be utilized, as indicated by the position of the fiducials. For free-breathing treatments, kV fluoroscopic images should be obtained to confirm the anticipated position of these fiducials during the entire respiratory cycle.
- 3) Active monitoring of treatment delivery accuracy using kV and/or MV projection imaging, either immediately before or during all (or a subset of) treatment fields.
- 4) Patient-specific dosimetric QA performed as per standard practice at each participating institution.

For SBRT, treatment should entail:

- 1) Initial orthogonal images obtained to confirm location of fiducial seeds.

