11.3 Adverse Events (AEs) and AE Monitoring

An AE is defined as any untoward medical occurrence in a clinical investigation subject, regardless of causal attribution.

All AEs should be graded according to the NCI Common Terminology Criteria for Adverse Events, Version 4.0, available at <http://ctep.cancer.gov/reporting/ctc.html>.

AEs should be:

- Assessed at each consultation or follow-up visit,
- Assessed during each mFFX cycle (prior to infusion is acceptable), and
- Recorded on the AE Tracking form in Appendix V.

Laboratory tests (CBC with differential and CMP) should also be obtained with each mFFX administration, and abnormal values also noted on the AE Tracking Form indicating AE Grade if applicable.

AEs should also be:

- Reported to Stanford as per protocol guideline and upon request
- Noted in patient study charts and binder
- Entered into REDCap CRFs
- Reported to the participating center's IRB as per their institutional guidelines.

AEs in REDCap CRF should remain current and may be requested by Stanford for study renewals, audits, reports, analyses or other submissions for Stanford IRB, SRC, or DSMC. AEs may also be reviewed by members of the study monitoring group in meetings, audits, and/or site visits.

Updates and outcomes of AEs, SAEs, UPs, and deviations may take place during teleconferences or more frequently as needed.

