14. STUDY CALENDAR

Activity	Induction Chemotherapy				Study Treatment	Follow-up (Time From Completion of Study Treatment) ^j							
	Screening	Study Enrollment	Induction Chemo / mFFX ^g	Re-staging ^c		SBRT ^d	mFFX 2 cycles ^f	4-8 wks ^k	3 ^j mos	6 ^j mos	9 ^j mos	12 ^j mos	Yr 2-Q 6 ^j mos
Biopsy	X				R								
Negative Pregnancy test ^a	X				A								
Consultation	X	X	X ^g		N			X ^k	X	X	X	X	X
ECOG PS	X	X			D			X ^k	X	X	X	X	X
Labs: CBCD, CMP, CA19-9 (CEA optional)	X	X ^b	X ^g		O		X ^h	X ^k	X	X	X	X	X
Study/research labs ⁱ (optional)		X ⁱ			M		X ⁱ	X ^k	X ⁱ	X ⁱ	X ⁱ	X ⁱ	X ⁱ
Eligibility		X			I								
Informed Consent		X			Z								
Study Registration		X			E								
QOL		X						X ^k	X	X	X	X	X
Scan: CT or MR	X			X ^c				X ^k	X	X	X	X	X
PET/CT ^e	X ^e								X ^e				
AE evaluation						X	X ^h	X ^k	X	X	X	X	X
Seed placement						X							
Meds: PPI and pain meds ^j								X ^k	X	X	X	X	X
Sim/setup scans						X							
SBRT						X ^d							
Maintenance mFOLFIRINOX ^{fh}								X-----X ^{fh}					

^a Pregnancy test by urine or serum, for women who are not post-menopausal as defined in Appendix III.

^b Labs should be done within 30 days of eligibility confirmation.

^c Re-staging scan should be done within 2 weeks following completion of induction mFOLFIRINOX cycles.

^d SBRT should begin within 4 weeks of simulation and 8 weeks of the last chemotherapy; dose is 40 Gy (8Gy in 5 fractions).

^e PET-CTs are recommended but not required; if only 1 follow-up PET-CT is possible, recommendation is at 3 months.

^f mFOLFIRINOX should resume within 8 weeks after study treatment, and any breaks between chemotherapy cycles should not exceed 8 weeks. Patients may continue on maintenance mFFX as tolerated or per clinical judgment of treating physician.

^g Induction chemo/mFFX prior to enrollment is allowed through the 4th cycle of mFFX. No more than 4 cycles are allowed prior to randomization. The re-staging scan could be done within 2 weeks of completion of the chemotherapy cycle; records from labs and clinic visits are not required; mFFX infusion records should be collected.

^h Labs during mFFX cycles are as per institutional standard or treating Medical Oncologist. AEs should be assessed with each cycle of mFFX.

ⁱ Study labs are optional and for research purposes as explained in Section 12. Correlative/Special Studies; and may be drawn if patient agrees to this in the consent form.

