- j Follow-up appointments 1 month before or after will be permitted, e.g. for 6-month follow-up, visit, labs, scan and QOL surveys can be done at 5-7 months.
- k 4-6 week follow-up visit and corresponding activities are *optional* and may be added if clinically indicated.

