17.1.2 Secondary Endpoints

- To compare the one year progression-free survival in pancreatic cancer patients following chemotherapy alone or chemotherapy and SBRT.
- To compare metastasis free survival in pancreatic cancer patients following chemotherapy alone or chemotherapy and SBRT.
- To compare the overall survival in pancreatic cancer patients treated with chemotherapy alone or chemotherapy and SBRT.
- To compare local progression-free survival in pancreatic cancer patients after chemotherapy +/- SBRT.
- To evaluate acute (within 3 months of treatment) grade 2 or greater gastritis, fistula, enteritis, or ulcer and any other grade 3-4 gastrointestinal toxicity within 3 months of treatment.
- To identify new biomarkers in pancreatic cancer.
- To evaluate the quality of life of patients before and after either chemotherapy alone or chemotherapy and SBRT.

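### No adverse-event check is required between SBRT and the resumption of mFFX, so acute GI toxicity may be recorded less completely in the SBRT arm

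*Combined protocol and SAP*

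**What the plan says.** AE assessment follows the chemotherapy cycle. Section 9.1 states "Subjects should be assessed for Adverse Events (AEs) once during each chemotherapy cycle" and sets the cycle length: "mFOLFIRINOX, 1 cycle = 14 days". Study Calendar footnote h repeats it: "AEs should be assessed with each cycle of mFFX". Section 11.3 has the same per-cycle rule and adds an assessment at every consultation or follow-up visit. The Calendar also marks an AE evaluation in the SBRT column.

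The arms then diverge. Section 5.3 says control patients "can continue directly with that treatment", with breaks of up to 8 weeks between cycles permitted. In the SBRT arm chemotherapy stops. Section 6.2 recommends 2-4 weeks between SBRT and chemotherapy and then adds: "However, it is acceptable to administer SBRT and chemotherapy within 8 weeks of each other". Section 7.1 sets the same 8-week limit for resuming mFFX.

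The one visit that could fall between SBRT and resumed mFFX is not required. Calendar footnote k says "4-6 week follow-up visit and corresponding activities are *optional", and Section 7.2 agrees. The Calendar column for that visit is headed 4-8 weeks, while 7.2 and footnote k say 4-6. Footnote j lets the 3-month visit take place a month early or late.

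The endpoint at issue, in Section 17.1.2, covers "acute (within 3 months of treatment) grade 2 or greater gastritis, fistula, enteritis, or ulcer", together with any other grade 3-4 GI toxicity in the same period.

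**The concern.** Non-serious toxicity is recorded mainly when someone asks about it. Here the asking is scheduled by mFFX cycle, and the experimental arm is by design off mFFX just after the experimental treatment. If early GI events are asked about less often in that arm, short-lived ones can go unrecorded there and be recorded in the other.

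Two analyses would be affected: the acute GI endpoint in 17.1.2, and the comparison of AE rates between treatment groups in 16.3. The direction would favour SBRT. The events most exposed are grade 2 gastritis, enteritis and ulcer, and grade 3 events that do not meet the SAE definition. The category is not trivial: Section 2.2 reports grade 2 ulcers in 15% of patients in an earlier single-fraction SBRT study. An event that was never asked about cannot be reliably recovered at analysis.

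**Working it through.** The plan states no number of AE checks, so there is no figure of its own to reproduce for the schedule. The count below uses its rules.

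**Inputs**
- Cycle length: 2 weeks (9.1).
- Gap G from SBRT to resumed mFFX: 2-4 weeks recommended (6.2), 8 weeks at most (6.2, 7.1).
- One AE evaluation at SBRT (Study Calendar), placed at week 0.
- Acute window: 3 months, taken as 13 weeks. It runs from treatment (17.1.2), so the clock starts at SBRT.
- The optional early visit is not counted. The 3-month visit is left out for both arms.

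**Formulas**
- SBRT arm: 1 check at SBRT, plus resumed cycles at weeks G, G+2, ... up to week 13, which is 1 + [floor((13 - G)/2) + 1].
- Control arm, uninterrupted, with a cycle at week 0: floor(13/2) + 1 = 7.

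| Gap G (weeks) | SBRT-arm checks | Uninterrupted control | Longest stretch without a required check, SBRT arm | Same, control |
|---|---|---|---|---|
| 2 | 1 + 6 = 7 | 7 | 2 weeks | 2 weeks |
| 3 | 1 + 6 = 7 | 7 | 3 weeks | 2 weeks |
| 4 | 1 + 5 = 6 | 7 | 4 weeks | 2 weeks |
| 8 | 1 + 3 = 4 | 7 | 8 weeks | 2 weeks |

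The unchecked stretch is 4/13 = 31% of the acute window for a 4-week gap and 8/13 = 62% for an 8-week gap, in both cases directly after SBRT.

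**If mFFX does not resume.** The next required check is the 3-month visit, which footnote j allows at 2 to 4 months. Held late, it leaves no required check after SBRT inside the 3-month window. For patients who miss the 8-week limit, 7.1 mentions follow-up for overall and progression-free survival but not for AEs.

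**A control patient on a permitted break.** A control patient who pauses for 8 weeks from week 0 has checks at weeks 0, 8, 10 and 12, which is 4, the same as the SBRT patient with the longest gap.

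**Stopping boundary.** Table 2 in 17.5.1 gives a 74.2% chance of triggering at a true toxicity rate of 20%. An exact binomial recursion on the Table 1 boundaries, n = 11 to 86, gives about 74%, so the figure reproduces. It presumes that every qualifying event is recorded. The documents give no ascertainment rate, so no reduced figure can be derived from them.

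**The case against.** The case on the other side has real force.

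- Checks are not tied to cycles alone. Section 11.3 adds every consultation and follow-up visit, and the Calendar has a check at SBRT itself. This stands, but none of these supplies a required check between SBRT and resumed mFFX.
- Two-weekly assessment in the control arm is nominal, because 5.3 allows breaks of up to 8 weeks and schedule changes are left to the oncologist. This also stands. The difference is that control breaks are discretionary, whereas the SBRT gap is part of the assigned treatment.
- On the recommended schedule the deficit is small: none in the count at 2 or 3 weeks, one check at 4. Eight weeks is the limit, not the norm.
- Events in the gap can be recorded at the first resumed cycle or at the 3-month visit, and a late visit does not move an early onset outside the window. This narrows the risk to events that have resolved and are forgotten or not dated.
- The acute GI endpoint is worded as an evaluation, not a comparison. However, 16.3 does compare AE rates between groups.

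Three stronger readings are tempting. A reader might count checks from randomization and find a much larger imbalance. The acute window runs from treatment, weeks before SBRT cannot hide SBRT toxicity, and the 8-week limit before SBRT runs from induction chemotherapy. A reader might take under-recording as established, but the documents show unequal opportunity to record, not missed events, and any capture rate would be an unsourced assumption. A reader might infer that the toxicity stopping guideline is seriously weakened. It concerns grade 3 or higher events over 6 months, a period that normally includes resumed cycles and the 3-month visit. Grade 3 and higher SAEs must be reported within 24 hours of being learned of (11.1.1), so any effect is probably small.

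**Conclusion.** The point holds in a limited form and is a cheap improvement. After the SBRT-column evaluation, no AE assessment is required until mFFX resumes or, failing that, until the 3-month visit. The resulting difference in required checks over 13 weeks from SBRT is 0 to 1 on the recommended schedule and 3 at the longest allowed gap, relative to an uninterrupted control patient. Short-lived grade 2 and non-serious grade 3 GI events may therefore be under-recorded in the SBRT arm, which could bias the acute GI endpoint and the 16.3 comparison toward SBRT looking safer.

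This rests on reading the Calendar's AE mark as one check at SBRT, on control cycles running to schedule, and on sites doing no more than is required. The size of any bias cannot be derived from the documents: they give neither the duration of such events nor the share later recalled.

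**What to change.** In 7.2, 11.3 and the Study Calendar (footnote k):

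- Make the AE evaluation in the existing early follow-up slot mandatory in both arms, with telephone contact allowed, whether or not mFFX is being given. The rest of that visit can stay optional.
- Set it at a matched time from randomization, chosen to fall after SBRT, so that both arms are asked at the same point.
- Reconcile the slot's timing, which is 4-8 weeks in the Calendar heading and 4-6 weeks in 7.2 and footnote k.
- Record an onset date for each AE, and count the acute endpoint by onset within the 3-month window and not by date of visit.

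This changes data collection only; treatment and its timing are untouched. The cost is protocol wording and about one short call per patient. Recorded SBRT toxicity may come out slightly higher than under the present schedule.

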9.1.1 Recommended Modifications for Toxicity

Below are recommendations and **not** requirements; **modifications of chemotherapy dose and schedule are allowed as per clinical judgment of patient's treating medical oncologist.**

9.1.1.1 Hematologic Toxicity

NOTE: mFOLFIRINOX dose modifications for hematologic toxicity are not based on CTCAE severity grades.

- For ANC 1,000/mm³–1,200/mm³: Delay mFOLFIRINOX until ANC > 1,200/mm³ then resume mFOLFIRINOX at the same dose level.
 - Second or More Occurrence of ANC 1000/mm³-1200/mm³: Delay mFOLFIRINOX until ANC > 1,200/mm³ then resume mFOLFIRINOX with one dose level reduction for all subsequent cycles. **NOTE:** The dose of leucovorin is not reduced.
- For ANC < 1,000/mm³: Delay mFOLFIRINOX until ANC > 1,200/mm³, then resume mFOLFIRINOX with one dose level reduction for all subsequent cycles. **NOTE:** The dose of leucovorin is not reduced.
- For Febrile Neutropenia (defined as ANC < 1,000/mm³ and temperature ≥ 100.5°F): Delay mFOLFIRINOX until resolution of fever and ANC > 1,200, then resume mFOLFIRINOX with one dose level reduction for all subsequent cycles. **NOTE:** The dose of leucovorin is not reduced.
- For Platelets 50,000 K/ul – 75,000 K/ul: Delay mFOLFIRINOX until platelets > 75,000 then resume mFOLFIRINOX at the same dose level.
 - Second or More Occurrence of platelets 50,000 K/ul - 75,000 K/ul: Delay mFOLFIRINOX until platelets > 75,000K/ul, then resume mFOLFIRINOX with one dose level reduction for all subsequent cycles. **NOTE:** The dose of leucovorin is not reduced.
- For Platelets < 50,000 K/ul: Delay mFOLFIRINOX until recovery to Plts > 75,000 K/ul then resume mFOLFIRINOX with one dose level reduction for all subsequent cycles. **NOTE:** The dose of leucovorin is not reduced.

9.1.1.2 Non-Hematologic Toxicity

Diarrhea

- For grade 2 Diarrhea (despite optimal medical management: see Section 9.1.3):
 - First Occurrence: Delay mFOLFIRINOX until recovery to grade ≤ 1 or baseline then resume mFOLFIRINOX at the same dose level.
 - Second or More Occurrence: Delay mFOLFIRINOX until recovery to grade ≤ 1 or baseline, then resume mFOLFIRINOX with one dose level reduction for all subsequent cycles. **NOTE:** The dose of leucovorin is not reduced.
- For grade 3 Diarrhea (despite optimal medical management: see Section 9.1.3):
 - First Occurrence: Delay mFOLFIRINOX until recovery to grade ≤ 1 or baseline, then resume 5-FU, leucovorin, and oxaliplatin, at the same dose level and irinotecan with one dose level reduction for all subsequent cycles.
 - Second or More Occurrence: Delay mFOLFIRINOX until recovery to grade ≤ 1 or baseline, then resume mFOLFIRINOX with one dose level reduction for all subsequent cycles. **NOTE:** The dose of leucovorin is not reduced.
- For grade 4 Diarrhea (despite optimal medical management): Delay mFOLFIRINOX until recovery to grade ≤ 1 or baseline then resume mFOLFIRINOX with one dose level reduction for all subsequent cycles. **NOTE:** The dose of leucovorin is not reduced.

Nausea/Vomiting

The following dose modifications are based on toxicity experienced during a cycle.

- For grade 3 Nausea/Vomiting (despite optimal medical management):
 - First Occurrence: Delay mFOLFIRINOX until recovery to grade ≤ 1 or baseline, then resume 5-FU and leucovorin, at the same dose level and oxaliplatin and irinotecan with one dose level reduction for all subsequent cycles.
 - Second or More Occurrence: Delay mFOLFIRINOX until recovery to grade ≤ 1 or baseline, then resume mFOLFIRINOX with one dose level reduction for all subsequent cycles. **NOTE:** The dose of leucovorin is not reduced.
- For grade 4 Nausea/Vomiting (despite optimal medical management): Delay mFOLFIRINOX until recovery to grade ≤ 1 or baseline, then resume mFOLFIRINOX with one dose level reduction for all subsequent cycles. **NOTE:** The dose of leucovorin is not reduced.

Mucositis

The following dose modifications are based on toxicity experienced at any time during a cycle.

- For grade 3 Mucositis:
 - First Occurrence: Delay mFOLFIRINOX until recovery to grade \leq 1, then resume irinotecan, oxaliplatin, and leucovorin at the same dose level and 5-FU with one dose level reduction for all subsequent cycles.
 - For Second or More Occurrence: Delay mFOLFIRINOX until recovery to grade \leq 1, then resume mFOLFIRINOX with one dose level reduction in irinotecan and oxaliplatin for all subsequent cycles. Dose of 5FU is reduced two dose levels for all subsequent cycles).
NOTE: The dose of leucovorin is not reduced.
- For grade 4 Mucositis:
Delay mFOLFIRINOX until recovery to grade \leq 1, then resume mFOLFIRINOX with one dose level reduction for all subsequent cycles.
NOTE: The dose of leucovorin is not reduced.

Peripheral Sensory Neuropathy

NOTE: Dose modifications for sensory neuropathy are **not** based on CTCAE severity grades.

- For paresthesia/dysethesia interfering with function and persisting between treatments: decrease oxaliplatin by one dose level for all subsequent cycles.
- For painful paresthesia/dysesthesia or symptoms that interfere with function and ADL, but improve (no longer painful or no longer interfering with ADL) between treatments: decrease oxaliplatin by one dose level for all subsequent cycles.
- For painful paresthesia/dysesthesia or symptoms that interfere with function and ADL that persists between treatments: Discontinue oxaliplatin.
- For persistent disabling or life-threatening paresthesia/dysesthesia: Discontinue oxaliplatin.
- For pharyngo-laryngeal dysesthesia: increase the duration of oxaliplatin infusion to 6 hours for subsequent cycles.

Oxaliplatin-induced pharyngolaryngeal dysesthesias

Should a patient develop oxaliplatin-induced pharyngolaryngeal dysesthesia, her/his oxygen saturation should be evaluated via a pulse oximeter; if normal, an anxiolytic agent may be given and the patient observed in the clinic until the episode has resolved. Following resolution of symptoms, patients may

continue/resume oxaliplatin if the reaction is NOT determined to be an allergic reaction.

A table comparing pharyngo-laryngodysesthesia to platinum hypersensitivity reactions is presented below.

Table 1 - Comparison of the Symptoms and Treatment of Pharyngolaryngodysesthesias and Platinum Hypersensitivity Reactions

Clinical Symptoms	Pharyngo-Laryngeal Dysesthesias	Platinum Hypersensitivity
Dyspnea	Present	Present
Bronchospasm	Absent	Present
Laryngospasm	Absent	Present
Anxiety	Present	Present
O2 saturation	Normal	Decreased
Difficulty swallowing	Present (loss of sensation)	Absent
Pruritis	Absent	Present
Urticaria/rash	Absent	Present
Cold-induced symptoms	Yes	No
Blood pressure	Normal or increased	Normal or decreased
Treatment	Anxiolytics, observation in a controlled clinical setting until symptoms abate or at the physician's discretion	Oxygen, steroids, epinephrine, bronchodilators; fluids and vasopressors, if appropriate

Venous Thrombembolic Events

- For grade 2 or 3 venous thromboembolic event: Continue mFOLFIRINOX at the same dose level. Do not use warfarin for therapeutic anticoagulation.
- For grade 4 venous thromboembolic event: Discontinue mFOLFIRINOX.

Liver Function Tests

- For grade 2 Increased Blood Bilirubin: Skip irinotecan until bilirubin improves to \leq grade 1.
 - For hyperbilirubinemia considered at least possibly related to irinotecan, then resume irinotecan with one dose level reduction for all subsequent cycles.
 - For hyperbilirubinemia considered unrelated to irinotecan, resume irinotecan at the previous dose level.
- For grade 3 or 4 Increased Blood Bilirubin: Delay mFOLFIRINOX until bilirubin improves to \leq grade 1. If bilirubin is thought to be due to a chemotherapy drug, then resume that drug at the next lower dose level

and the other drugs at the same dose level when total bilirubin improves to \leq grade 1.

- For hyperbilirubinemia considered at least possibly related to treatment (any drug) resume mFOLFIRINOX with one dose level reduction in suspect drug(s) for all subsequent cycles.
- For hyperbilirubinemia considered unrelated to treatment (all drugs), resume mFOLFIRINOX at the previous dose levels.

Allergic Reactions

- For grade 2 allergic reactions: Interrupt infusion(s). Manage reaction according to institutional policy. Restart the infusion(s) when symptoms resolve to \leq grade 1 and pre-treat before all subsequent doses.
- For grade 3 or Grade 4 allergic reactions: Discontinue infusion. Manage reaction according to institutional policy. Discontinue mFOLFIRINOX.

Irinotecan dosing and UGT1A1*28 allele homozygosity

Caution should be exercised when dosing irinotecan in patients who express homozygous for the UGT1A1*28 allele. The toxicity is dose-dependent. The FDA recommends reducing the dose by one dose level for patients expressing UGT1A1*28 allele. For additional information, please refer to the package insert.

Other non-hematologic toxicities

- For all other grade 3 non-hematologic toxicities considered at least possibly related to mFOLFIRINOX: Skip the responsible drug(s) until toxicity improves to \leq grade 1, then resume the responsible drug(s) with one dose level reduction for all subsequent cycles.
- For grade 4 non-hematologic toxicities considered at least possibly related to mFOLFIRINOX: Discontinue the responsible drug(s).

